5. DATA AND SPECIMEN BANKING*

REDCap will be used to store research data stored as subject code (PHI such as infant/child and maternal medical histories, daily clinical care measurements) and analyzed data (i.e., scored sleep studies; actigraph and physiological data). Physiological and environmental (light/sound) data collected on acquisition system and actigraph data may also be stored on excel worksheets on password protected computers for post-hoc analysis.

It is possible that the data will be shared with collaborating investigators (e.g., engineers and programmers) to assist with signal processing and analysis, with the NEATCap device manufacturer and/or other manufacturers who may be involved with the development or commercialization of either devices, and investigators not associated with this project. If so, all data will be stripped of all identifiers (anonymized) and subjects' identity will be unknown to these personnel. De-identified information may be made available in the future for the research community using NIH-sponsored websites, in accordance to NIH mandated data sharing policy. Any investigator contacting us for such data will be directed to the appropriate website(s), which has detailed instructions on the use of the data in accordance with NIH policies. Subject may choose to have research data anonymized at any time during or at the end of the study by contacting [name] at [contact] (or via email at [contact]).

- *Disclosure of Research Results:* This study is for research purposes only. Individual results will not be given back to study participants nor will individual results go into subjects' medical record. In the short term, we do not anticipate that any clinically or diagnostically important information can be learned from this research, although such information could eventually be forthcoming.

6. DATA ANALYSIS AND MANAGEMENT*

Statistical Procedures and Power Analysis.

Study design will allow systematic quantification (mean and variance) of the effects of NEATCap device and SVS mattress on automatic function, such as breathing (IBI), cardiac rhythm (R-R), frequency and duration of body movements (e.g., defined via streamlined video, artifact in pulse-oximeter plethysmographic activity, and actigraph count), blood oxygenation (e.g., durations<85%), skin temperature, and sleep states. Analyses will be conducted to determine whether interventions impinge on neural oscillators that drive breathing and cardiac control, and whether NEATCap device reduces dangerous levels of environmental noise, to improve autonomic function and sleep activity.

NCT03881553 Study Protocol and Statistical Analysis Plan

Signal processing algorithms will be used to characterize separately the instability of physiological signals, such as respiration and heartbeat. We will explore, for example, whether different durations of movement periods (e.g., 1.5-5 sec; >5 sec; >10sec) have unique relationships with withdrawal (NAS or iatrogenic) or prematurity, and are affected differently with different interventions (NEATCap device and SVS Mattress).

Parametric tests will be used for analyses of all continuous variables. The Friedman's and Wilcoxon signed-rank tests will be used for nonparametric analyses. For analyses of parametric data separate repeated measures ANOVAs will test effects of stimulus condition (ON or OFF) and trial order. Post-hoc pairwise t-tests will determine differences in responses for conditions of stimulation ON and OFF. For example, separate repeated measures ANOVAs will test effects of stimulus condition (ON or OFF) and trial order on physiological variables. Time of intervention (e.g., infant age, severity of NAS) will be a covariate to assess whether there are critical periods in infant development for optimizing the intervention as a therapeutic strategy. Pearson product-moment correlation coefficient analysis will be used to establish associations between breathing stability (IBI variance) and movement duration, with the expectation that greater variance in respiratory parameters will be positively correlated with excessive movement. *P* values of <0.05 will be considered significant.

The number of periods and duration of intervention will not always be the same for each study session. The proposed study will test if different modes (NEATCap; Mattress SVS) affects duration of the interfeed interval, improves autonomic function, and promotes sleep. This is a within-subjects design, so all subjects will receive intervals of routine clinical care in addition to the assigned intervention/s complementary to routine care. Intervention assignment for study session is based on equipment availability, research personnel availability; it will not be determined by the subject's treating physician.

- It is possible that a subject does not receive an intervention (participate in a study session) after enrollment if: 1) We have technical difficulties and are unable to conduct studies; 2) Subject is discharged before being entered into an intervention stimulation session; 3) Doctor treating child requests we terminate the study – we will heed to the discretion of the Attending Physician or primary medical caregiver for decisions regarding termination of an infant from the study for example due to sickness, sepsis or exacerbated withdrawal symptoms (e.g., seizures) – such population of subjects will likely already be excluded by the exclusion criteria, but others unknown at this time may also ensue. Medical criteria for terminating a subject from the study will be determined by the medical caregiver treating the infant. Authorized parent, nurse or investigator may stop/postpone a study session for reasons such as excessive symptomatology preventing ability to properly study the subject (e.g., unable to keep sensors in place, infant needs to be held incessantly, skin rash), parent has visitors or simply doesn't want an infant/child studied on a particular day – this would not result in termination from the study per se. If we find that a mode of stimulation appears to make the infant/child irritable (e.g., excessive waking, crying, movement), we will end the study session for that day. If this happens on a second study-session day, we will discontinue study.

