Standard measurements and recordings. Physiologic recordings with and without electroencephalographic (EEG) activity will be obtained through state-of-art acquisition system (e.g., Embla, Nihonkohden or other) obtained (hardcopy) or recorded (digital) directly from hospital monitor (e.g., Philips, ixTrend or other). Respiratory inductance plethysmography (RIP) will be used to measure breathing. Respiratory belts will be placed around the chest wall and/or abdomen to record respiratory muscle movements, and allow for detection of inter-breath intervals (IBI) of respiration. Sensors over the skin surface of the torso will be used to record electrocardiographic activity (ECG), and allow for detection of R-R intervals of the ECG signal (index of inter-beat heart rate). Electrodes over the head and face area will be used to measure EEG activity at the surface of the cortex to allow for sleep stage classification using EEG signal analysis; electrode impedance will be measured to help ensure data quality. A probe attached to the foot or wrist will measure arterial-blood oxygen concentration; quality of the plethysmographic activity characterized in the pulse signal will allow for identification of movement periods. Movement periods will be assessed further via actigraphy with a wireless sensor worn around the infant's leg and/or arm that records limb movement. Skin temperature will be measured continuously with a sensor placed under the armpit or back. A sound and light meter placed near the head will record sound frequency and intensity, and changes in light level. Overt behavioral data will be recorded using a camera with a wide-angled lens placed within or near the subject's bed. Medical history (including toxicology screens) and demographic data will be obtained on the infant/child and on the biological mother by manual medical record review or electronically extracted via UMCCTS Data Lake.

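### The ON–OFF tests of breathing and heart-rhythm variability ignore sleep state, so they cannot show whether the devices act on the underlying oscillators

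*Combined protocol and SAP*

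**What the plan says.** Section 6 (Statistical Procedures and Power Analysis) lists breathing, cardiac rhythm and sleep states side by side as outcomes. It then states a question about mechanism: "Analyses will be conducted to determine whether interventions impinge on neural oscillators that drive breathing and cardiac control".

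The analysis offered is this: "separate repeated measures ANOVAs will test effects of stimulus condition (ON or OFF) and trial order on physiological variables". The only adjustment named is "Time of intervention (e.g., infant age, severity of NAS) will be a covariate". The threshold is that P "values of <0.05 will be considered significant". Later in the same section, the study is also to test whether the devices affect the interval between feeds, and whether each mode "improves autonomic function, and promotes sleep".

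Section 4 (Standard measurements and recordings) says that EEG is collected "to allow for sleep stage classification using EEG signal analysis". It also says "Physiologic recordings with and without electroencephalographic (EEG) activity will be obtained", so staging will not be available for every recording. Section 4 (Study Sessions) allows some sessions to be recorded straight from the bedside monitor.

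No section stratifies, restricts or adjusts the IBI or R-R analyses by sleep state. No section defines which part of an ON or OFF period is analysed.

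**The concern.** Variability measured over a stretch of recording that contains several behavioural states is a mixture. It depends on the variability inside each state and on the share of time spent in each. A device could change the first, the second or both. Only the first is evidence of a direct action on the control of breathing or heart rhythm.

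The plan itself treats a change in sleep as a possible device effect. An ANOVA on condition and trial order returns one ON–OFF difference per variable and cannot say which route produced it. The planned Pearson correlation of IBI variance with movement duration does not help, because it does not separate sleep state from the device contrast.

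At stake is the mechanistic conclusion. An ON–OFF difference reported as an oscillator effect could be the sleep result seen through a second variable.

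**Working it through.** **No figure to reproduce.** Although its heading mentions power, Section 6 gives no sample size, effect size or SD, and no variability by state. What follows illustrates size only; every input is an assumption.

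**Mixture formula.** Let q be the share of time in the lower-variance state, with variance set to 1. Let r be the variance in the remaining time relative to it. With equal mean intervals in both,

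pooled variance = q × 1 + (1 − q) × r.

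The device is given no effect inside either state; ON changes only q.

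| r | q 0.40 → 0.50 | change | q 0.50 → 0.60 | change |
|---|---|---|---|---|
| 1 | 1.00 → 1.00 | 0% | 1.00 → 1.00 | 0% |
| 1.5 | 1.30 → 1.25 | −3.8% | 1.25 → 1.20 | −4.0% |
| 2 | 1.60 → 1.50 | −6.2% | 1.50 → 1.40 | −6.7% |
| 3 | 2.20 → 2.00 | −9.1% | 2.00 → 1.80 | −10.0% |
| 4 | 2.80 → 2.50 | −10.7% | 2.50 → 2.20 | −12.0% |
| 6 | 4.00 → 3.50 | −12.5% | 3.50 → 3.00 | −14.3% |

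If q does not change, every row gives 0%. If the device disturbs sleep, the sign reverses: at r = 2, q falling from 0.50 to 0.40 gives 1.50 → 1.60, or +6.7%.

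**Unequal means.** If mean intervals differ between states by d, a term q(1 − q)d² is added. Its coefficient moves from 0.24 to 0.25 for the first shift (0.40 × 0.60 to 0.50 × 0.50) and back from 0.25 to 0.24 for the second. It can therefore offset or reinforce the change, and it is left out of the table.

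**What a test would do.** A simulation used a paired t-test on log pooled variance (5,000 runs, two-sided 0.05). It assumed two ON and two OFF periods per child, q = 0.50 under OFF and 0.60 under ON, an SD of 0.12 for q between periods, and an SD of 0.25 for log variance within state. The device again had no within-state effect. Rejection rates:

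| Children | r = 1 | r = 1.5 | r = 2 | r = 3 |
|---|---|---|---|---|
| 20 | 5% | 15% | 29% | 48% |
| 40 | 5% | 25% | 55% | 79% |
| 80 | 5% | 47% | 83% | 98% |

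With q unchanged, the rate was about 5% throughout. The same comparison made within one state rejected in 4.5% to 5.8% of runs across all scenarios. That simulation has no selection of epochs by the device, so it shows the within-state contrast under favourable conditions.

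**The case against.** The case on the other side has real force.

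- **The plan does not say that it pools across states.** A reader might infer that IBI and R-R are analysed over whole periods, because recording runs through the session and the factor is ON or OFF. The analysis window is simply not stated. This is a gap in specification, not a declared choice. The point stands because nothing in the plan requires any other analysis.
- **An artefact is not certain.** A reader might infer that a device acting only on sleep will show up as an oscillator effect. That needs a difference in variability between states and a detectable shift in the state mix, and the documents quantify neither. The nearest support is that Section 6 expects more variable breathing to go with more movement. That concerns movement, not sleep state, and has no size attached. Section 6 also foresees a device that makes a child wake more, which would push the difference the other way.
- **The main comparison is sound.** The mechanistic sentence goes on to speak of improving autonomic function and sleep, and for those questions an ON–OFF difference is a legitimate total effect. A reader might also infer that the plan will count autonomic and sleep gains as two independent benefits; it nowhere says so.
- **The remedy has its own weakness.** Sleep state is measured after the device is switched on. The epochs of a given state under ON and OFF need not be comparable, and a child without that state in one condition contributes nothing.

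The first three objections limit the point to the oscillator clause. The fourth means that a within-state result is better evidence on mechanism, not proof.

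**Conclusion.** The concern holds for the mechanistic claim only. As specified, the IBI and R-R analyses cannot separate a direct effect on breathing or cardiac control from a change in the mix of sleep states. The ON–OFF contrast is not invalidated, and the documents do not show that a false oscillator effect will occur.

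The possible size runs from 0%, if the state variances are equal or the mix is unchanged, to a fall of about 4% to 12.5% for a 10-point rise from 40% in the lower-variance state with variance ratios of 1.5 to 6. Starting from 50%, the range is 4.0% to 14.3%. These figures rest on assumed shares and ratios, equal means across states and no within-state effect. The rejection rates also rest on assumed SDs and sample sizes; they are not estimates for this trial.

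The plan should be changed on this point, because the aim is explicit and the data needed are already collected wherever EEG is recorded.

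**What to change.** 1. Keep the ON–OFF contrast of IBI and R-R, labelled as the total effect, and state which part of each period enters it.
2. For sessions with EEG staging, add a secondary ON-versus-OFF comparison of IBI and R-R variability. Compute it in fixed-length epochs labelled by scored state and compare within the same state, with state as a repeated factor or through a within-child state-standardised mean.
3. Limit statements about oscillators or direct autonomic control to that contrast. Add the caveat that state is measured after the intervention starts, so the epochs compared may be selected.
4. For sessions without EEG, report the total effect only.

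The cost is analysis wording and some programming; no new data are needed. The price is fewer usable minutes per state, wider intervals, loss of children who lack a state in one condition, and a mechanistic claim confined to EEG sessions.

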 - 2) **SVS Mattress Device:** The SVS mattress device is an experimental device. It will be used to gently stimulate the subject. The specially-constructed mattresses are similar to the usual hospital mattress except that inside the mattress foam there is a device that vibrates the foam, controlled by an external unit. The mattresses are constructed by Cofab Design, LLC or other contracted company using patent specifications, modified to adjust for various size cribs and beds. The device components in the mattress and external control unit may be modified with improved technologies to allow for testing of various displacements and mattress sizes, and to help ensure consistency of mattress integrity over time. The mattresses are designed so that the foam vibrates throughout the entire mattress. We are aware of no deleterious effects of the SVS mattress. We have studied over 100 premature infants (since 2001) and over 50 infants exposed to opioids *in utero* (since 2010) using the SVS mattress without incident or apparent side effects. The FDA has not approved the SVS mattress as a treatment for prematurity or withdrawal. Sound level produced by the mattress will be monitored and will not exceed 75 decibels (60-70 dB is normal conversation; 75 dB is about the sound of an average car interior on a highway). The UMass/Memorial Health Care Biomedical Engineering will certify the electrical safety of the mattress devices.
- **Research procedures:** Subjects will participate in up to four sessions, applying either the NEATCap and/or SVS mattress. Sessions will last on average between 8 and 12 hours, and will not exceed 24 hours in any one session. All sessions will

NCT03881553 Study Protocol and Statistical Analysis Plan

be performed at the subject's NICU/CCN or PICU/PIU bedside. Infants and children enrolled in this study will receive routine, standard of care, which may include pharmacological management as prescribed by their primary medical caregiver complementary to the intervention (NEATCap; SVS mattress). Nurses are instructed to provide routine care and to intervene as they would typically do despite the presence of an investigator by the bedside.

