Study Sessions. The study will be conducted in the UMass Memorial NICU/CCN and in the UMass Memorial Children's Medical Center PICU/PIU. The subject will be studied in the unit in which he/she is receiving care. Enrollment in this study allows the subject to participate in up to 4 full-recording study sessions throughout their hospitalization. A full-recording study session will typically last approximately 8-12 hours (~8am-6pm or ~8pm-6am); some sessions may start earlier/later or go shorter/longer and in some instances we may study the subject for 24 hours (based on research personnel and equipment availability). The reasoning behind a shorter session and for having morning and evening start times is that as the subject matures, s/he may have 'wakeful' periods that prevent study in the crib/bed for certain periods throughout the day. The reasoning behind a 24-hr period is if we have available research-personnel support, we may study a subject throughout a complete 24-hr period to obtain diurnal responses. The number of full-recording sessions the subject participates will depend on duration of hospitalization (e.g., some subjects may be in the hospital longer than others, which will allow more opportunity to participate in multiple study sessions), on availability of research equipment and research personnel, and parent/guardian schedule (e.g., parent/guardian may prefer we not study the subject on certain days, for example if they want to spend time holding the subject or have visitors throughout the day). We will review the infant's/child's medical records and we will obtain additional history through questionnaire from the consenting parent/guardian. We will also obtain medical history on the subject's biological mother, including questionnaire and review of maternal medical records, if available through the UMass Memorial Healthcare system.

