Sessions will begin during the infant's/child's feeding, assessment or wake period, during which time sensors for the full-physiology/polysomnography recording will be applied by research study staff; sessions may begin any time if recordings are obtained directly from the bedside monitor. Periods of no intervention (NEATCap device OFF or SVS Mattress OFF) will be alternated with periods of intervention on (NEATCap device ON or SVS Mattress ON). The duration of each intervention period will conform to the routine care of the study subject. Because feeds vary as a function of subject's age, for example premature infants are typically on a fixed ~every 3-4 hours, whereas older infants and children may feed ad-libitum (i.e., as the child desires), the duration of intervention ON and OFF will vary within and between sessions and among subjects. The hospital standard of care for an individual subject, and the subject's sleep/wake cycle will determine the duration of the intervention periods. For subjects who may sleep throughout the night, periods of intervention will conform to either a routine assessment or medication interval (typically ~ every 3-4 hours) to allow for comparisons between intervention ON and intervention OFF with minimal disruption to the subject. The OFF-ON alternating cycles allow subjects to serve as their own control and ascertain if intervention ON leads to consistent, positive responses in the same subject, and assess whether the effect changes over the period.

NEATCap Intervention: At feed/assessment/wake period preceding a

NCT03881553 Study Protocol and Statistical Analysis Plan

NEATCap ON period, the NEATCap device will be fitted and placed on the child by research study staff. The NEATCap device will be removed (OFF) and replaced (ON) at alternating intervals throughout the study session. Physiological data will be recorded throughout the session while the subject is in the crib/bed or hospital-issued sleeping environment (e.g., motorized seat).

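### Repeated-measures ANOVA on condition and an undefined trial order does not fit the planned unequal sessions and periods; define order and use a mixed model

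*Combined protocol and SAP*

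**What the plan says.** **Analysis (section 6, Statistical Procedures and Power Analysis).** The parametric plan is: "For analyses of parametric data separate repeated measures ANOVAs will test effects of stimulus condition (ON or OFF) and trial order". Post-hoc pairwise t-tests compare ON with OFF. Friedman and Wilcoxon signed-rank tests are listed for nonparametric analyses in general. Age and NAS severity at the time of intervention enter as covariates, to look for critical periods. Trial order is not defined, and there is no aggregation rule, missing-cell rule or session term.

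**Data structure (sections 4 and 6).**
- Sessions per child: up to four, with either or both devices. "The number of full-recording sessions the subject participates will depend on duration of hospitalization", and also on staff, equipment and the parents' schedule.
- Session length: "Sessions will last on average between 8 and 12 hours, and will not exceed 24 hours in any one session"; under Study Sessions, "in some instances we may study the subject for 24 hours".
- Period length: "the duration of intervention ON and OFF will vary within and between sessions and among subjects". On feeding, "premature infants are typically on a fixed ~every 3-4 hours, whereas older infants and children may feed ad-libitum".
- Number of periods: section 6 itself says that "The number of periods and duration of intervention will not always be the same for each study session".

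**Purpose of alternating (section 4, Study Sessions).** The OFF-ON cycles are meant to "ascertain if intervention ON leads to consistent, positive responses in the same subject, and assess whether the effect changes over the period".

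**The concern.** A classical repeated-measures ANOVA with condition and order as within-child factors uses only children who have every condition-by-order cell. Here the cells will differ between children by design, and section 6 acknowledges this without saying how the ANOVA will cope.

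Because trial order is undefined, the consequence depends on the reading:
- **Across sessions:** children with fewer sessions lack cells, so children or cycles must be discarded.
- **Cycle within session:** ordinary sessions contain one complete OFF-ON cycle, so order has a single level. Later cycles exist only in long sessions.
- **Period position within session:** if every session starts in the same condition, position and condition cannot be separated in two-period sessions.

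At stake are precision under the first reading and, under the other two, the order test itself. The question of whether the effect changes over time is then left without a workable planned analysis.

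**Working it through.** The documents give no sample size, variance or power figure, so there is no stated result to reproduce. The checks use the documents' time ranges plus assumptions marked as such.

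**1. Periods per session.** Inputs from section 4: session length S of 8-12 h and period length D of 3-4 h. Assumption: both uniform. The number of complete periods is floor(S/D).
- 2D lies between 6 and 8 h, so two periods always fit. 4D lies between 12 and 16 h, so four fit only at the exact extreme of 12 h and 3 h.
- P(three periods) = P(S ≥ 3D) = E[(12 − 3D)/4] = (12 − 10.5)/4 = 37.5%. P(two periods) = 62.5%.
- A 24 h session holds 24/4 = 6 to 24/3 = 8 periods.

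**2. Order counted across sessions.** Assumptions: one cycle per session, residual variance 1, and variance τ² of the ON effect between children of 0 or 0.5. A child with c cycles has ON-OFF variance v = τ² + 2/c. An ANOVA on k cycles keeps children with c ≥ k and uses k cycles from each.

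Variance ratio = E[1/v] ÷ {P(c ≥ k)/(τ² + 2/k)}.

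For 1-4 sessions equally likely and τ² = 0: E[1/v] = (0.5 + 1 + 1.5 + 2)/4 = 1.25. For k = 2 the ratio is 1.25/(0.75/1) = 1.67. For k = 4 it is 1.25/(0.25/0.5) = 2.50.

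| Children with 1/2/3/4 sessions | k = 2 (τ² = 0 / 0.5) | k = 3 | k = 4 |
|---|---|---|---|
| 25/25/25/25% | 1.67 / 1.46 | 1.67 / 1.71 | 2.50 / 2.92 |
| 40/30/20/10% | 1.67 / 1.58 | 2.22 / 2.46 | 5.00 / 6.31 |
| 10/20/30/40% | 1.67 / 1.38 | 1.43 / 1.38 | 1.88 / 2.08 |

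In the first row the ANOVA keeps 75%, 50% or 25% of children.

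**3. Order counted within session.** From step 1, an ordinary session has one complete cycle, so a cycle factor has one level. If sessions always start OFF, condition is a function of position. A rank check of categorical position plus condition, with up to six periods, gave rank 6 for 7 columns: complete aliasing. With a linear position term, only the third and later periods separate the two.

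**4. What a mixed model does and does not repair.** Assumptions: all sessions start OFF; no true ON effect; a step of 0.4 residual SD after the first period.
- In an OFF-ON-OFF session the linear slope is 0.4/2 = 0.20 per period, so the linear-position model reports an ON effect of 0.4 − 0.20 = 0.20.
- A paired comparison sees 0.4 in two-period sessions and 0.4 − 0.4/2 = 0.20 in three-period sessions. Weighted by session this is 0.625 × 0.4 + 0.375 × 0.20 = 0.325; on child means it is 0.31.
- A first-period indicator has no bias under the step, but it is biased by minus one period's drift under linear drift, and its SE is 1.34 times as large.

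**5. Precision.** Assumptions: SDs of 1 (child), 0.5 (child-by-condition), 0.5 (session) and 1 (residual); 1-4 sessions equally likely; 30 children. The SE of the ON effect is about 0.192 for the linear-position mixed model and 0.197 for the child-level paired test; (0.192/0.197)² = 0.95, about 5% in variance. The SE of condition-by-session number is about 0.16 residual SD per session (0.20 with 20 children, 0.11 with 60).

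**6. Child clustering.** With child-by-condition variance of 0.25, 0.5 or 1.0, dropping that random effect raised type I error to 7.9%, 10.4% or 14.3%. Dropping session within child left it at 5.0%.

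**The case against.** The main ON-OFF comparison does not depend on the ANOVA. Section 6 also plans pairwise t-tests and Wilcoxon tests. On one ON and one OFF mean per child these are valid when there is no time trend (simulated type I error 5.0%, 5.4% and 4.9% with 20, 30 and 60 children). Data loss arises only if order is counted across sessions, and the session distributions behind 1.4-6.3 are assumed. The mixed model barely improves precision and does not cure confounding with time. All of this stands and limits the point to the order test and the data lost under one reading.

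The one-cycle result counts only complete periods, and the 3-4 h figure is tied to premature infants' feeds and to overnight assessment or medication intervals. Counting a part-period at the end gives three or four periods per session. That too stands, but the cells would still differ between children.

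Some stronger readings are tempting, and the documents do not support them:
- That Friedman will test trial order. Section 6 ties order only to the ANOVAs. Friedman meets the complete-block problem only if applied to several periods per child.
- That raw totals will be compared over unequal periods. No time scale is stated, so neither totals nor rates can be presumed.
- That age and severity enter as main effects only. The stated aim of finding critical periods suggests an interaction; the text simply does not say.

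**Conclusion.** The concern holds for the order analysis and should be fixed. The planned ANOVA and the planned data structure do not match, and this follows from the text without any assumed figure. Under the across-session reading the cost is discarded data, illustratively a variance 1.4 to 6.3 times that of an analysis of all cycles. Under the within-session readings the order test cannot be run in ordinary sessions, or it coincides with condition in two-period sessions if all start in the same condition, which is not stated.

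A reader might infer that the ON-OFF comparison is invalid. It is not: as a paired test on child means it stands when there is no time trend. A reader might also infer that a mixed model settles whether the effect changes over the period. It does so only in part. Section 4 uses the word period both for a session and for an ON or OFF interval, and neither is session number. Change across sessions can be estimated, though imprecisely: with 30 children, 80% power needs about (1.96 + 0.84) × 0.16 = 0.45 residual SD per session. Change within a session can be estimated only where sessions are long enough.

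All magnitudes rest on assumed session distributions and variances.

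**What to change.** 1. Define trial order as period position within session, plus session number. Take each session's starting condition from the logs already described in section 4 (Data acquisition, recording and archival).
2. Replace the ANOVA with one linear mixed model per continuous outcome on all period-level data. Fixed effects: condition by device (with a level for sessions using both devices), linear position, session number, and age or NAS severity at the session. Random effects: child, child-by-condition and, where estimable, session within child, with small-sample degrees of freedom. If the model must be simplified, always keep child-level clustering of the ON effect.
3. State that critical periods are tested by condition-by-age (or severity), and change in effect across sessions by condition-by-session number. Report condition-by-position only where sessions are long enough, and say that within-session change is otherwise not estimable.
4. If all sessions start OFF, state that the ON effect is separated from time only by assuming a trend shape. Report a sensitivity model with a first-period indicator in place of linear position.
5. Report the child-level paired comparison as a check. Keep data recorded up to an early stop and report stops by condition; the stopping rule itself is not at issue.
6. Optional clarification: express accumulating outcomes per recorded hour.

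The cost is SAP wording and more programming, with no new data collection. The downsides are reliance on a modelled time trend, little gain in precision for the main ON effect, and imprecise interaction estimates.
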